# 6.1. Study setting

The study will be carried out in six research sites (clusters), reflecting a range of National Health Service (NHS) practice to allow for generalisability.

### 6.1.1. Community settings

Three community services will be used for recruitment:

- Primary care
- Paramedics
- Admiral nurses

The first setting will be in primary care: patients with a known diagnosis of dementia presenting with a fall in the last 6 months, at participating practices in the Clinical Commissioning Groups (CCGs) involved in the study.

Potential participants will also be identified by paramedics attending calls to a person with possible dementia presenting with a fall. This will apply to calls within the postcodes served by the participating CCGs.

Admiral nurses will identify patients with possible dementia, resident within the postcodes served by participating CCGs, who seek or have sought healthcare attention regarding a fall within the past 6 months.

Page 27 of 59

# 6.1.2. **Secondary care settings**

Four secondary care services will also identify potential study participants:

- Emergency departments
- Supported discharge teams
- Rehabilitation outreach teams
- Memory clinics

Patients with possible dementia presenting with a fall in the last 6 months to any of these services in participating Trusts will be eligible if they are resident within the postcodes served by participating CCGs.

## 6.1.3. Research registers

We will also recruit potential participants from local research case registers. Participants on the case register have already given consent to be approached about potential research projects. Those registered with either service will be eligible for the study if they have had a fall within the last 6 months.

Join Dementia Research (JDR) can be utilised for participant recruitment. JDR is an on-line self-registration service that enables volunteers with memory problems or dementia, carers of those with memory problems or dementia and healthy volunteers to register their interest in taking part in research. The purpose of JDR is to allow such volunteers to be identified by researchers as potentially eligible for their studies. Researchers can then contact volunteers, in line with the volunteers preferred method of contact, to further discuss potential inclusion.

## 6.2. Participant eligibility criteria

Participants are PWD on the Primary Care Quality Outcomes Framework (QOF) Dementia register who have sustained at least one fall within six months prior to identification as a study participant. Recruitment will include patients presenting to community settings (primary care, admiral nurses, paramedics), patients presenting to secondary care settings (emergency departments, rehabilitation teams, mental health services) and patients listed on research registers. Carers will be screened and recruited to the study as a pair with the patient participant.

Carers are either a close family member or friend who receive no financial compensation for the care they provide to the patient participant. The PWD and their family members or friends will determine who will be identified as the carer for the study.

See Section 7.1.3 for details of professional participants who will be invited to take part in the embedded qualitative process evaluation.

#### 6.2.1. **Inclusion criteria patient participants**

1. A diagnosis of dementia made prior to entry into the study. PWD must be on the Primary Care Quality Outcomes Framework (QOF) Dementia register.

Page 28 of 59

- 2. Must have sustained at least one fall within 6 months prior to identification as a potential study participant. A fall is defined as an event whereby a person comes to lie on the ground or another lower level with or without loss of consciousness.
- 3. Must be dwelling in their own home at the time of the index fall and returning to their own home at the time of the intervention.
- 4. Must have an unpaid carer available to assist with completion of the diaries.
- 5. Either has capacity to consent to participation, or a personal or nominated consultee who is able to give an opinion on the participation of the PWD.
- 6. Able to communicate in English
- 7. Aged over 50 years.

## 6.2.2. Exclusion criteria patient participants

- 1. Diagnosis of dementia cannot be confirmed by the primary care team within 4 weeks of their being identified.
- 2. PWD found to be dwelling in a care home, or to have been a hospital inpatient at the time of the index fall.
- 3. PWD refuses consent, or lacks capacity and does not have personal or nominated consultee, or their personal or nominated consultee declines participation.
- 4. Unpaid carer declines participation in the study

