#### Definite Go ('green light'):

- ≥ 40% of eligible patients consenting to pilot trial
- ≥ 80% participants attend ≥ 60% of sessions as planned
- Retention of ≥ 70% of consented participants for key outcome data at 6 months
- An indication from qualitative work that the intervention is perceived as acceptable to both participants and professionals.

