### Definite Stop ('red light'):

- < 10% of eligible participants consenting to pilot trial

- < 30% participants attend ≥ 60% of sessions as planned in a given intervention arm
- retention of < 50% of consented participants for provision of key outcome data at 6 months
- It is clear from the process data from participants and professionals that the intervention procedures have low fidelity in terms of content, frequency, duration and quality and/or that the intervention is not feasible to deliver.

Intermediate targets will be defined as amber and refinement of the study will be undertaken in conjunction with our PPIE panel and other key stakeholders. A decision as to whether to progress to planning a full trial will be discussed by the Trial Steering Committee.

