# 7.1.1.1. Community Services

Within primary care services, a retrospective search will take place at the beginning of the study to identify potential participants who have had a fall in the last 6 months. An invitation letter and a participant information sheet (PIS) will be sent to the potential participant, explaining what the study is about and that they are eligible to take part. Dementia QOF registered patients will have a flag applied to their records. During primary care consultations with these potential participants, the professional will be alerted to determine if the patient's fall occurred within the last 6 months and if so, the patient can be given an invitation letter and PIS. Potential participants will be approached no more than once about the study. District and practice nurses will be included in the Site Initiation Visit (SIV) to ensure they are prepared to discuss the study with patients who are seen in their homes. Any potential participants who receive the invitation letter can complete and return an opt-in form to the clinical researcher if they are interested in taking part.

Other community settings include admiral nurses and paramedics. Patients presenting with a history of memory problems and a fall requiring healthcare attention will receive the introductory letter and PIS from the relevant service. Potential participants with a history of memory problems can be self-reported, reported by an informal carer, recorded in service records, or on observation. Potential participants can complete and return an opt-in form to the clinical researcher if they are interested in taking part. Potential patients taken to hospital by paramedics will be identified at the emergency department (ED) by the secondary care team. Therefore, paramedics will only identify and give the introductory letter and PIS to potential participants that are not taken to hospital to avoid multiple contacts with the patient. If the potential participant is in a distressed state, paramedics will be asked to use their discretion when considering giving the patient the letter and PIS as it may be inappropriate at that time. If a potential participant lacks capacity to understand the PIS and introductory letter from undue stress, and a carer is not present, these documents will not be given.

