# 7.1.4. Confirmation of PWD eligibility

The research team will confirm that the PWD is on the primary care QOF dementia register prior to formal recruitment to the study, with the exception of potential participants identified through primary care. Once the potential participant has received the PIS they will be contacted by the clinical researcher via telephone call. During this initial telephone call to discuss participation, the clinical researcher will obtain verbal consent from the PWD to contact their GP practice to check whether the potential participant is on the dementia QOF register. For those referred directly by primary care, we will already know that the participant is on the dementia QOF register.

If the potential participant is on the QOF register, the clinical researcher will contact them again to confirm eligibility and, if the PWD is still interested, to arrange a home visit to take consent and undertake baseline assessment. Potential participants who are not on the dementia QOF register will be sent a letter explaining that they are not eligible by thanking them for their interest.

The clinical researcher will be asked to keep a list of all potential participants who have had contact with the research study team at each stage of the recruitment process. If the potential participant has declined or not responded to a contact from the research team, or if they have not been recruited for any other reason, they will not receive any further contacts from the research team.

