# 9. Statistics and data analysis

### 9.1. Sample size calculation

We will randomise six rehabilitation services (clusters), one in each of 6 sites, and aim to recruit 60 PWD altogether (3 services and 30 PWD to each of the intervention and the control arms). Each service will recruit 10 PWD during the 6-month recruitment period, based on a recruitment rate of 1.7 PWD per service per month as achieved during our feasibility study. If recruitment is slower than expected, we will consider adding 2 additional sites.

The sample size calculation was based on the precision for estimating the proportion of eligible people that consent to participate in the study. We anticipate that we will have to approach 150 eligible people and 40% (60 participants) of these will agree to take part. The 150 who are screened is a large enough number to estimate the percentage that consent with a 95% confidence interval 29% to 51%. If the percentage that is followed up is 80%, 60 recruited participants is large enough to estimate this with a 95% confidence interval 66% to 91%, and the 30 participants in the intervention arm is large enough to estimate the percentage that attends at least 60% of the allocated sessions with a 95% confidence interval 60% to 93%. These confidence intervals take clustering into account [16] and are based on an assumed intra-cluster (intra-service) correlation coefficient of 0.05 to quantify variability across clusters in the feasibility parameters (i.e., percentage consented, followed-up, attending at least 60% of sessions).

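### The Stop/Go consent rate has an inconsistent denominator that, outside the primary-care route, is selected for interest

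*Protocol*

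**What the plan says.** **The criterion.** Protocol 4.4 sets green at or above "40% of eligible patients consenting to pilot trial" and red below "10% of eligible participants consenting to pilot trial". SAP 5.1 and SAP Table 5 carry the same proportion without defining the denominator.

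**The planning figure.** Protocol 9.1, repeated in SAP 2.3, says: "We anticipate that we will have to approach 150 eligible people and 40% (60 participants) of these will agree to take part". The next sentence calls the same people screened: "The 150 who are screened is a large enough number to estimate the percentage that consent".

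**Who is eligible.** Protocol 6.2.2 lists as exclusion 3 "PWD refuses consent, or lacks capacity and does not have personal or nominated consultee, or their personal or nominated consultee declines participation" and as exclusion 4 "Unpaid carer declines participation in the study". SAP 4.2 defines eligibility by dementia, age, residence, register status and a recent fall, and is silent on refusal. SAP 5.2 estimates the eligible share of those screened and the consenting share of those eligible as two separate percentages.

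**When eligibility becomes known.** Protocol 7.1.4 places the register check in the telephone call about participation, where "the clinical researcher will obtain verbal consent from the PWD to contact their GP practice to check whether" the person is on the dementia register. The exception is people referred by primary care, whose register status is already known. In the community routes (Protocol 7.1.1.1), people given a letter "can complete and return an opt-in form to the clinical researcher if they are interested in taking part". Protocol 7.1.1 lets each site choose which routes it uses.

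**The concern.** There are two separate problems.

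First, the documents conflict. Under 6.2.2 a person who refuses is excluded; under 9.1 the same person is one of the 90 eligible people who do not agree.

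Second, resolving that conflict in the SAP's favour does not settle the denominator. SAP 4.2 still requires register status, and outside primary care nobody learns that status until the person has agreed to the check. Someone who declines on the call, cannot be reached, or never returns an opt-in form cannot be shown to meet the definition. Exclusion 1 in 6.2.2 points the same way, because it removes anyone whose diagnosis primary care does not confirm within four weeks of identification. Neither document says how these people are classed.

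Two decisions depend on this. The Trial Steering Committee reads the rate against 40% and 10%, and the full trial will use it to judge how many people it must approach. The rate by arm is also one of the checks for recruitment bias by unblinded research nurses (Objective E; Protocol 9.2, SAP 5.2). If route mix differs between arms, the percentages can differ with no difference in uptake.

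**Working it through.** **1. The plan's own figure.** Inputs from Protocol 9.1: 150 eligible approached, 60 agree, 6 clusters, intra-cluster correlation 0.05.

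- Rate: 60/150 = 40%.
- Average cluster size: 150/6 = 25. Design effect: 1 + (25 − 1) × 0.05 = 2.20. Effective sample size: 150/2.20 = 68.2.
- Wald 95% interval: 0.40 ± 1.96 × √(0.40 × 0.60/68.2) = 28.4% to 51.6%. A Jeffreys interval gives 29.0% to 51.8%.

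The stated interval is 29% to 51%, so it reproduces to within about one percentage point. It does so with the 150 − 60 = 90 people who do not agree inside the denominator.

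**2. Exclusions 3 and 4 applied literally.** All 90 leave the denominator: 60/60 = 100%. The red rule could then never be met. This shows that 6.2.2 and 9.1 cannot both define the denominator.

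**3. Effect of counting only confirmed-eligible people.** Let N be the number truly eligible, 60 the number consenting, and f the share of eligible non-consenters who drop out of view before the register check. Then

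reported rate = 60 / [60 + (N − 60)(1 − f)].

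N and f are not in the documents, so these are scenarios:

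| True rate (N) | f = 0 | f = 1/4 | f = 1/2 | f = 3/4 |
|---|---|---|---|---|
| 40% (150) | 40.0% | 47.1% | 57.1% | 72.7% |
| 30% (200) | 30.0% | 36.4% | 46.2% | 63.2% |
| 20% (300) | 20.0% | 25.0% | 33.3% | 50.0% |
| 15% (400) | 15.0% | 19.0% | 26.1% | 41.4% |

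**4. Loss needed to reach green.** Setting the reported rate to 40% for a true rate p gives f = 1 − 1.5p/(1 − p).

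- p = 30%: 1 − 0.45/0.70 = 36%
- p = 25%: 1 − 0.375/0.75 = 50%
- p = 20%: 1 − 0.30/0.80 = 62.5%
- p = 15%: 1 − 0.225/0.85 = 73.5%

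**5. Dependence on route.** Suppose two arms each approach 150 eligible people and 30 consent, so both have a true rate of 20%. If one arm recruits wholly through primary care and its silent invitees are counted, it reports 30/150 = 20%. If the other uses only routes where half of the 120 non-consenters are never checked, it reports 30/(30 + 60) = 33%. The 13-point gap contains no recruitment bias. The example is deliberately extreme; it shows the mechanism, not an expected size.

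**The case against.** The strongest reply is that the documents already separate eligibility from consent. SAP 4.2 leaves refusal out, SAP 5.2 models the two as different outcomes, SAP 4.3 reports decliners with reasons in the flow diagram, and the sample size counts refusers as eligible. That stands. A reader might infer from 6.2.2 that the rate will be 100%, or that it is inflated by construction. The documents do not support that reading: an item in an exclusion list bars enrolment, and the analysis text points the other way. What remains of the first problem is a conflict in wording.

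A reader might also infer that eligibility is always confirmed only after a person shows interest. That is too broad. Register status is known in advance on the primary-care route, and in secondary care the researcher's call does not wait for a reply. The call is still where permission for the register check is sought, however, so people who decline on it or are not reached remain unconfirmed.

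Nor is the overall direction fixed. Counting every unconfirmed person as eligible would push the rate down, because some were approached with only possible dementia and may not be on the register. The upward bias applies to a confirmed-eligible denominator on the routes outside primary care.

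Finally, consent is one of four criteria, with an amber zone and a committee decision, and Objective E also draws on participant characteristics and loss to follow-up. That limits the consequence but does not supply a denominator.

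**Conclusion.** The point holds in limited form. The Stop/Go denominator is inconsistent between Protocol 6.2.2 and Protocol 9.1, SAP 2.3 and SAP 4.2. Outside primary care, the only people who can be confirmed eligible are those who agreed to be checked. On those routes a confirmed-eligible rate is biased upward; across all routes it depends on each site's mix, which weakens the by-arm comparison.

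The size cannot be derived from the documents. It rests on the assumed loss before confirmation: a true 25% reads as green at 50% loss and a true 20% only at 62.5%, while at half lost a true 20% reads as 33% and stays amber. A false green is therefore possible but not shown to be likely.

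One caveat: the protocol supplied is Version 3.0 and the SAP cites Version 5.0, so the exclusion wording may have changed.

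**What to change.** **In SAP 5.1 and Table 5:**

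- State that refusal by the person, consultee or carer counts as eligible non-consent. Keep people who lack capacity and have no consultee as ineligible.
- Report the rate on two denominators: (a) confirmed eligible; (b) confirmed eligible plus those who declined or did not respond before the register check and were not shown to be ineligible.
- For (b), give the none-eligible and all-eligible bounds and, labelled as an assumption, an estimate using the route-specific fraction found eligible among those checked. For example, with 60 consenting, 80 confirmed-eligible decliners and 160 never checked, the bounds are 60/140 = 43% and 60/300 = 20%.
- Show both by arm and by route where the data allow.
- Have the Trial Steering Committee read the 40% and 10% thresholds against this range, not against (a) alone.

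**In the wording:** reconcile 6.2.2 with 9.1 and SAP 4.2, after checking Protocol Version 5.0, and change *screened* to *eligible* in the precision sentence of 9.1 and SAP 2.3.

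**Cost.** Mostly text, but not only text. The list in Protocol 7.1.4 covers people in contact with the research team, so invitation counts for opt-in routes may have to come from the referring services. Protocol 10.1 limits what the university keeps on non-consenters and does not list route. The SAP was written during follow-up, so some counts may be only partly recoverable. The reported figure will be wider or less favourable.

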#### 6.2.3. Inclusion criteria carer participants

- 1. Family member or friend of the PWD patient participant.
- 2. In contact with patient participant for at least one hour per week.
- 3. Able to communicate in English sufficiently well to complete the proxy outcome measures.
- 4. Has capacity to provide informed consent.

#### 6.2.4. Exclusion criteria carer participants

There are no exclusion criteria for carer participants.

Page 29 of 59

# 7. Trial procedures

#### 7.1. Recruitment

# 7.1.1. Participant Identification

The following settings will be available as routes for participant identification. Study sites will determine which settings are logistically available and do not have to utilise all settings. If the routes outlined do not fall under the study site's trust, they will be set up as PIC sites i.e. paramedic, admiral nurses, memory clinic, rehabilitation outreach teams and primary care. PICs will be identified as site set-up commences.

# 7.1.1.1. Community Services

Within primary care services, a retrospective search will take place at the beginning of the study to identify potential participants who have had a fall in the last 6 months. An invitation letter and a participant information sheet (PIS) will be sent to the potential participant, explaining what the study is about and that they are eligible to take part. Dementia QOF registered patients will have a flag applied to their records. During primary care consultations with these potential participants, the professional will be alerted to determine if the patient's fall occurred within the last 6 months and if so, the patient can be given an invitation letter and PIS. Potential participants will be approached no more than once about the study. District and practice nurses will be included in the Site Initiation Visit (SIV) to ensure they are prepared to discuss the study with patients who are seen in their homes. Any potential participants who receive the invitation letter can complete and return an opt-in form to the clinical researcher if they are interested in taking part.

Other community settings include admiral nurses and paramedics. Patients presenting with a history of memory problems and a fall requiring healthcare attention will receive the introductory letter and PIS from the relevant service. Potential participants with a history of memory problems can be self-reported, reported by an informal carer, recorded in service records, or on observation. Potential participants can complete and return an opt-in form to the clinical researcher if they are interested in taking part. Potential patients taken to hospital by paramedics will be identified at the emergency department (ED) by the secondary care team. Therefore, paramedics will only identify and give the introductory letter and PIS to potential participants that are not taken to hospital to avoid multiple contacts with the patient. If the potential participant is in a distressed state, paramedics will be asked to use their discretion when considering giving the patient the letter and PIS as it may be inappropriate at that time. If a potential participant lacks capacity to understand the PIS and introductory letter from undue stress, and a carer is not present, these documents will not be given.

The research team will keep in regular contact with all participating services to make sure they remain aware of the study and are able to identify and resolve any issues to recruitment.

Page 30 of 59

# 7.1.1.3. Research registers

At some sites a database of research interested patients with a diagnosis of dementia who have given consent to be approached about research studies is maintained. Staff will identify potential participants from the Case Register. The initial approach will be made by phone by a member of the research staff who will introduce the study and check whether the person has had a fall in the last 6 months. If the patient has had a fall and is potentially interested in taking part, their verbal consent will be sought to pass their contact details to the clinical researcher. The clinical researcher will then send out the introductory letter and PIS and follow this up with a telephone call approximately one week later. The clinical researcher will answer any questions and check whether they are still interested in taking part in the study having had time to consider the information in the PIS. If appropriate, a home visit will be arranged at which consent will be sought and the baseline assessment completed.

